1.1 Study design

This is a Phase III multicenter, randomized, double-blind, placebo-controlled study to demonstrate superiority of ligelizumab 72 mg and/or 120 mg sc q4w over placebo as an add-on therapy to H1-antihistamines at local-approved doses in adults and adolescents for the treatment of Chronic Inducible Urticaria (CINDU). The study will be approximately 40 weeks in duration with the primary endpoint assessed at Week 12. There are 3 subtypes of CINDU populations being assessed in three parallel cohorts: symptomatic dermographism, cold urticaria and cholinergic urticaria. The study consists of 3 distinct periods:

Screening period (Day - 28 to Day 0): Duration of up to 4 weeks in which participants who have given informed consent are assessed for eligibility.

Treatment period (24 weeks): There are 7 visits during this period. Participants will receive treatment at 6 visits (Week 0, Week 4, Week 8, Week 12, Week 16 and Week 20). Week 24 is the End of Treatment visit; no treatment will be given at this visit. Provocation testing will be done at Week 0, Week 4, Week 8, Week 12 and Week 24.

Follow-up period (12 weeks): The participants should be seen in the clinic every 4 weeks until Week 36. There will be no study treatment administered at these visits; provocation testing will be done at Week 36 only.

On 06 April 2022, following extensive assessment of data from the Phase III studies of ligelizumab in CSU, Novartis communicated a strategic decision to discontinue further clinical development of ligelizumab in chronic urticaria (CSU and chronic inducible urticaria (CINDU)). The decision to not proceed was not based on any safety concerns with ligelizumab. As a result of this decision, this study CQGE031E12301 was terminated. At the time of study termination 39 participants were enrolled in the study.

1.1.1 Screening

Screening was stopped as of 6th April 2022.

As per protocol, the screening period was up to 4 weeks. The screening period can be shortened depending on the availability of the laboratory results and adherence to wash-outs related to non-allowed medication. Only in exceptional circumstances, when information concerning eligibility is outstanding (e.g., pending laboratory data), will an extended period be permitted. Along with the participant's background medication, participants will also be allowed to take rescue medication (non-sedating H1-AH) on an as needed basis for unbearable symptoms from screening up to the end of the study.

Rescreening may be allowed for participants who failed initial screening. Only 1 rescreening will be allowed. If a participant is rescreened for the study, the participant must sign a new informed consent and will be issued a new participant number. Informed consent for a rescreened participant must be obtained prior to performing any study-related assessments or collecting any data for the Screening visit.

1.1.2 Double-blinded treatment period

As a result of study termination, all subjects in the treatment phase were discontinued from treatment and moved into the follow-up phase. Only 3 subjects had completed Week 12 visit.

Below is a description of the treatment period as per protocol:

Symptomatic dermatographism and cold urticaria cohorts: On Day 1, participants were randomized equally into ligelizumab 120mg vs ligelizumab 72 mg vs placebo, with participants in the placebo arm being randomly re-allocated to ligelizumab 120 mg and ligelizumab 72 mg at week 12. Randomization will only be performed once at Day 1, in a 2:2:1:1 fashion into 4 arms: ligelizumab 120 mg, ligelizumab 72 mg, placebo to ligelizumab 120 mg and placebo to ligelizumab 72 mg.

During the treatment period, doses are administered at 6 visits: Week 0, Week 4, Week 8, Week 12, Week 16 and Week 20. Participants randomized to the placebo arm will receive placebo for the first three treatment visits; Week 0, Week 4 and Week 8 and will then switch to ligelizumab 120 mg q4w or ligelizumab 72 mg q4w (1:1 ratio) for the remaining 3 treatment visits; Week 12, Week 16 and Week 20. Participants will continue to use their stable background therapy (H1-AH) at stable doses during the study.

Cholinergic urticaria cohort: On Day 1, participants will be randomized into a 1:1 fashion to ligelizumab 120 mg q4w vs. placebo. Participants of the placebo arm will be allocated to ligelizumab 120 mg at Week 12. Participants of the cholinergic urticaria cohort will not receive the ligelizumab 72 mg dose. During the treatment period, doses are administered at 6 visits: Week 0, Week 4, Week 8, Week 12, Week 16 and Week 20. Participants randomized to the placebo arm will receive placebo for the first three treatment visits; Week 0, Week 4 and Week 8 and will then switch to ligelizumab 120 mg q4w for the remaining 3 treatment visits; Week 12, Week 16 and Week 20. Participants will continue to use their stable background therapy (H1-AH) at stable doses during the study.

At weeks 0, 4, 8, 12, 24 and 36 participants from all cohorts will be subjected to provocation tests in order to elicit symptoms. A positive response at Week 0 (Day 1) to the FricTest^{®4.0}, TempTest^{®4.0} or Pulse Controlled Ergometry is required to be randomized to the symptomatic dermatographism, cold urticaria or cholinergic urticaria cohorts, respectively. Based on medical history, if a participant has more than one form of inducible urticaria (example: symptomatic dermatographism and cold urticaria) then the participant must be considered for randomization into the group that is most bothersome to the participant. Since thresholds are not defined in CINDU, it is left to the investigator's judgement to enroll only those participants with moderate or severe disease burden.

For the symptomatic dermatographism cohort, it is planned to allocate approximately 168 participants so that each treatment arm has 56 participants. For the cold urticaria cohort, it is planned to allocate approximately 102 participants so that each treatment arm has 34 patients. For the cholinergic urticaria, it is planned to allocate approximately 158 participants so that each treatment arm has 79 participants. For details on the calculation of the sample size for each of the three cohorts, see Section 3.

Due to the low prevalence of this indication among the three cohorts, it is plausible that not all cohorts will be able reach their planned sample size, requiring modification of the sample size and modification to the statistical analysis with different data cut-offs for the different cohorts.

Follow-up period

[figure not shown]
The follow-up period is 12 weeks with the last follow-up visit (Week 36) corresponding to 16 weeks after the last treatment dose. No study treatment will be given during the post-treatment follow-up period. Participants will continue with the background medication and will be allowed to take their rescue medication on an as needed basis, [REDACTED]. Participants will be required to visit the study center every 4 weeks during post-treatment / follow-up period.

Remote procedures

As per section 4.6 of the study protocol, during a Public Health emergency as declared by Local or Regional authorities i.e., pandemic, epidemic or natural disaster, that may challenge the ability to ensure participant safety and trial integrity, the option of conducting the entire visit 170 and visit 180 remotely may be offered to participants. For any other visit it may also be possible to conduct certain assessments for safety and efficacy remotely as described within Section 8. Any assessment performed remotely will be performed under the oversight of the

Investigator, who retains accountability for the oversight and all efficacy and safety decisions with delegation of tasks to an off-site healthcare professional. The remote procedures will be offered in certain countries and sites as determined by Novartis based on national and local regulations. The off-site healthcare professionals whether provided by Novartis or by the site must be agreed with Novartis before use.

Figure 1-1 Study design

[figure not shown]

[figure not shown]
1.2 Study objectives, endpoints and estimands

[figure not shown]
Table 1-1 Objectives and related endpoints

Objective(s)	Endpoint(s)
Primary objective(s)	Endpoint(s) for primary objective(s)
To demonstrate superiority of ligelizumab versus placebo with regards to the change from baseline in response to a standardized provocation test for each CINDU subtype	
Symptomatic Dermographism Change from baseline in Total Fric Score (TFS) at Week 12 in response to FricTest® 4.0
 
Cold Urticaria Change from baseline in critical temperature threshold (CTT) at Week 12 in response to the TempTest® 4.0
 
Cholinergic Urticaria Change from baseline in itch numerical rating scale (NRS) at Week 12 in response to the pulse-controlled ergometry test.

Objective(s)	Endpoint(s)
Secondary objective(s)	Endpoint(s) for secondary objective(s)

To demonstrate superiority of ligelizumab versus placebo with regard to proportion of participants with a complete response after standardized provocation test
	
Symptomatic Dermographism
 
Proportion of participants with complete response in FricTest® at Week 12
 
Change from baseline in itch NRS following provocation test at Week 12, in participants with itch NRS > 0 at baseline

To demonstrate superiority of ligelizumab versus placebo in itch NRS following the provocation test.
	
Cold Urticaria
 
Proportion of participants with complete response in TempTest® at Week 12
 
Change from baseline in itch NRS following provocation test at Week 12, in participants with itch NRS > 0 at baseline
 
Cholinergic Urticaria
 
Proportion of participants with itch NRS=0 following the pulse-controlled ergometry test at Week 12
 
Proportion of participants with physician global assessment of severity of hives=0 following the pulse-controlled ergometry test at Week 12

To assess the safety of ligelizumab
	
Safety endpoints will include but not be limited to:
 
 • Occurrence of treatment emergent adverse events (serious and non-serious) during the study • Occurrence of treatment emergent adverse events during the study leading to discontinuation of study treatment • Occurrence of treatment emergent adverse events of interest listed as either identified or potential risks, during the study • Changes in safety parameters

1.2.1 Primary estimand(s)

The estimand is the precise description of the treatment effect and reflects strategies to address events occurring during trial conduct which could impact the interpretation of the trial results (e.g premature discontinuation of treatment).

For each subtype of CINDU, the primary clinical question of interest is: what is the treatment effect of the ligelizumab treatment versus placebo on the primary endpoint in participants with H1-AH as background medication, regardless of use of rescue medications and/or prohibited medications and treatment discontinuations due to either AE, or use of prohibited medications, or lack of efficacy, assuming that participants had never discontinued treatment due to other reasons or missed any treatment prior to Week 12 due to other non-human controlled emergency situations (e.g. COVID-19).

The justification for the primary estimand is that it will capture both the effect of the study drug and the effect of additional background and rescue medications, mirroring the conditions in clinical practice. This will also enable an estimation of the effect of study drug for the full duration of the study. Further details can be found in study protocol section 5.

The primary estimand for each of the CINDU cohort is described by the following attributes:

- **Population:** participants receiving H1-antihistamines therapy at local-approved dose level as background medication suffering from symptomatic dermatographism, cold urticaria, or cholinergic urticaria and meeting study inclusion/exclusion criteria (as listed in study protocol Section 5.1 and 5.2). Further details about the population are provided in study protocol section 5.
- **Endpoint:**
 1. Symptomatic Dermatographism: change from baseline to Week 12 in Total Fric Score (TFS, i.e., score derived based on results from the Fric Test 4.0, see study protocol Section 8.3.1.1 for details)

2. Cold urticaria: change from baseline to Week 12 in critical temperature thresholds (CTT, i.e. the highest temperature hives are triggered, see study protocol Section 8.3.1.2 for details) in response to the TempTest[®]
 3. Cholinergic urticaria: change from baseline to Week 12 in itch numerical rating scale (itch NRS) in response to the pulse-controlled ergometry (see study protocol Section 8.3.1.3 for details).
- **Treatment of interest:** ligelizumab or the placebo treatment (no further treatment for patients who discontinue treatment due to AE, lack of efficacy or intake of prohibited medications) with stable H1-antihistamines at local-approved doses as background medication + allowed rescue medication. The dose of the allowed background medication for CINDU must remain stable during the trial. Further details about the investigational treatment and control treatment are provided in study protocol Section 6.
 - **Handling of remaining intercurrent events:**
 - Discontinuation of initial assigned study treatment prior to Week 12 due to either adverse events (AE), or use of prohibited medications, or lack of efficacy (LoE): Participants who discontinue from study treatment early will be encouraged to stay in the study as detailed in study protocol Section 9.1.1. Retrieved drop out (RDO) data collected after study treatment discontinuation will be used for analysis. (*treatment policy*).
 - Discontinuation of initial assigned study treatment prior to Week 12 due to reasons other than adverse events (AE), use of prohibited medications, or lack of efficacy (LoE): had participants taken the assigned treatment up to Week 12 (*hypothetical strategy*)
 - Use of prohibited medications prior to Week 12 and not result in treatment discontinuation: ignore (*treatment policy*)
 - Missed treatment prior to Week 12 due to other non-human controlled emergency situations (e.g. COVID-19): had participants not missed treatment prior to Week 12 other non-human controlled emergency situations (*hypothetical strategy*)
 - **The summary measure:**
 1. Symptomatic Dermographism: difference in mean change from baseline in Total Fric Score at Week 12 between treatments (ligelizumab 72 mg q4w vs placebo and ligelizumab 120 mg q4w vs placebo)
 2. Cold urticaria: difference in mean change from baseline of CTT at Week 12 between treatments (ligelizumab 72 mg q4w vs placebo and ligelizumab 120 mg q4w vs placebo)
 - 3. Cholinergic urticaria: difference in mean change from baseline in itch NRS in response to the pulse-controlled ergometry test at Week 12 between treatments (ligelizumab 120 mg q4w vs placebo)

1.2.2 Secondary estimand(s)

For each subtype of CINDU, the secondary clinical questions of interest are similar as the primary clinical questions of interest and are based on the secondary endpoints. The only

difference is that, for the endpoint of complete responder status, participants with discontinuation of initially assigned study treatment prior to Week 12 due to either AEs, or use of prohibited medications, or lack of efficacy (LoE) will be considered as non-responders (i.e. composite strategy).

The secondary estimand for each of the CINDU cohort is described by the following attributes:

- **Population:** participants receiving H1-antihistamines therapy at local-approved dose level as background medication suffering from symptomatic dermatographism, cold urticaria, or cholinergic urticaria and meeting study inclusion/exclusion criteria (as listed in study protocol Section 5.1 and 5.2).

- **Endpoints:**

Symptomatic dermatographism:

1. proportion of participants achieving complete response (i.e. TFS = 0) in the FricTest[®]4.0 at week 12.
2. change from baseline to Week 12 in itch numeric rating scale (NRS) following the FricTest[®]4.0.

Cold urticaria:

1. proportion of participants achieving complete response (a negative provocation test result for the lowest temperature (4°C) in TempTest[®]4.0 at week 12.
2. change from baseline to Week 12 in itch numeric rating scale (NRS) following the TempTest[®]4.0.

Cholinergic urticaria:

1. proportion of participants achieving complete response in itch NRS (itch NRS =0) following the pulse-controlled ergometry test at Week 12.
 2. proportion of participants achieving complete response in physician global assessment of severity of hives (i.e. PGA hive score=0) following the pulse-controlled ergometry test at week 12.
- **Treatment of interest:** ligelizumab or the placebo treatment (no further treatment for patients who discontinue treatment due to AE, lack of efficacy or intake of prohibited medications) with stable H1-antihistamines at local-approved doses as background medication + allowed rescue medication. The dose of the allowed background medication for CINDU must remain stable during the trial.
 - **Handling of remaining intercurrent events:**
 1. Discontinuation of initial assigned study treatment prior to Week 12 due to either adverse events (AE), or use of prohibited medications, or lack of efficacy (LoE):
 - a. For continuous endpoints “change from baseline to Week 12 in itch NRS following provocation tests” (applicable to symptomatic dermatographism and cold urticaria cohorts): participants who discontinue from study treatment early will be encouraged to stay in the study as detailed in study protocol Section 9.1.1.

Retrieved drop out (RDO) data collected after study treatment discontinuation will be used for analysis (*treatment policy*).

- b. For binary endpoints (see table below): participants with discontinuation of initially assigned study treatment prior to Week 12 due to AEs, use of prohibited medications or lack of efficacy (LoE) will be considered as non-responders. (*composite strategy*).

Cohort	Endpoints

 • symptomatic dermographism • cold urticaria 	proportion of participants achieving complete response at Week 12 in response to provocation tests

 • cholinergic urticaria 	proportion of participants achieving complete response in itch NRS (itch NRS =0) following the pulse-controlled ergometry test at Week 12 proportion of participants achieving complete response in physician global assessment of severity of hives (i.e. PGA hive score=0) following the pulse-controlled ergometry test at week 12

2. Discontinuation of initial assigned study treatment prior to Week 12 due to reasons other than adverse events (AE), use of prohibited medications, or lack of efficacy (LoE): had participants taken the assigned treatment up to Week 12 (*hypothetical strategy*)
3. Use of prohibited medications prior to Week 12 and not result in treatment discontinuation: ignore (*treatment policy*)
4. Missed treatment prior to Week 12 due to other non-human controlled emergency situations (e.g. COVID-19): had participants not missed treatment prior to Week 12 other non-human controlled emergency situations (*hypothetical strategy*)

• **The summary measure:**

Symptomatic dermographism and cold urticaria:

1. difference in complete response rates at Week 12 between treatments (ligelizumab 72 mg q4w vs placebo and ligelizumab 120 mg q4w vs placebo)
2. difference in mean change from baseline of itch NRS following provocation tests at Week 12 between treatments (ligelizumab 72 mg q4w vs placebo and ligelizumab 120 mg q4w vs placebo)

Cholinergic urticaria:

1. difference in proportion of participants achieving itch NRS=0 at week 12 between treatments (ligelizumab 120 mg q4w vs placebo)
2. difference in proportion of participants achieving PGA hive score=0 at week 12 between treatments (ligelizumab 120 mg q4w vs placebo)

- Ligelizumab 72 mg q4w
- Ligelizumab 120 mg q4w
- Placebo – Ligelizumab 72 mg q4w
- Placebo – Ligelizumab 120 mg q4w

For cholinergic urticaria cohort, study treatment groups used for analysis are defined as below:

- Ligelizumab 120 mg q4w
- Placebo – Ligelizumab 120 mg q4w

2.1.1.2 Study Day 1 and other study days

The first day of administration of randomized study treatment (first dose) is defined as *study Day1* or *Day 1*.

[figure not shown]
All other study days will be labeled relative to Day 1. For event dates on or after Day 1, study day for a particular event date will be calculated as [Date of event] - [Date of first dose] + 1. For the dates before Day 1, study day for an event date will be calculated as [Date of event] - [Date of first dose].

Duration of an event will be calculated as (Event end date - Event start date + 1).

The descriptor “Day 0” will not be used.

2.1.1.3 Study Week based on RaveX collected visit information

For efficacy and safety data collected by eCRF at scheduled visit (provocation test outcomes, lab results, ECGs, vital signs, PROs, [REDACTED] etc.), study week will be defined based on the visit name. For by visit summary tables, all the information collected at the scheduled visit will be included for the analyses. Unscheduled visit information will not be included in the by visit summary descriptive statistics. The unscheduled visit information will be only included in the maximum or minimum post treatment assessment summaries.

2.1.1.5 Screening, baseline, and post-baseline

Screening refers to any procedures (e.g., checking inclusion and exclusion criteria) performed prior to the first dose of study treatment. Per protocol, subject informed consent must be obtained prior to performing any study related activity. The date of signing informed consent is the start date of screening period. Any assessment obtained during the screening period will be labeled screening assessment. Assessments made on Day 1 may occur before or after the first dose.

For efficacy analyses based on the provocation tests, baseline is the last assessment (including unscheduled visits) obtained on the randomization day.

All assessments obtained after randomization are considered as post-baseline unless otherwise specified.

For safety analyses (e.g., lab, vital sign assessments etc), baseline is the last assessment (including unscheduled visits) obtained (on or) before the first dose (day) of study treatment. For a subject who receives partial dose for the first dose day of study treatment, the baseline will still be defined according to the first dosing date of the partial dose. For a subject without any administration of study dose, the baseline assessment will be his/her last assessment under the study. If multiple assessments are taken on the same date, then the pre-dosing assessment closest to the dosing time (i.e., the latest recorded time prior to the dosing time on that date) will be used for baseline. If the recorded time parts of duplicated assessments are the same or missing, then the averaged outcome of the duplicated assessment on that date will be used for baseline. All assessments obtained after the first dose (day) of study treatment are considered as post-baseline unless otherwise specified.

Handling of multiple assessment on the same date, on the last date on or before treatment start date:

- ECG measurements: the worst outcome of them will be used for baseline.

[REDACTED]

[REDACTED]

[REDACTED]

[REDACTED]

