#### **8.4.2 Electrocardiogram (ECG)**

Standard 12 lead ECGs must be recorded after 10 minutes rest in the supine position to ensure a stable baseline. The preferred sequence of cardiovascular data collection during study visits is ECG collection first, followed by vital signs, and blood sampling. The Fridericia QT correction formula (QTcF) should be used for clinical decisions.

Single local 12 lead ECGs will be collected at Screening (Visit 1), Week 24 (Visit 160) and unscheduled as required.

The Fridericia QT correction formula (QTcF) must be used for clinical decisions, e.g., at the Screening (as applicable) to assess eligibility. The investigator must calculate QTcF if it is not auto-calculated by the ECG machine.

The original ECG will be sent electronically to the Clinical Research Organization (CRO) directly from the provided ECG machine. Two “identical” duplicate print-outs will be generated on non-heat sensitive paper and kept at the investigator site as source documentation and as back-up for submission to the vendor in case of problems with the electronic transmission. The “identical” duplicates must be labeled with study number, participant initials, participant number, date and time, and signed and archived in the study site source documents.

Clinically significant ECG findings prior to dosing with study drug treatment must be discussed with the sponsor. Additional, unscheduled, safety ECGs may be repeated at the discretion of the investigator at any time during the study as clinically indicated. For any ECGs with participant safety concerns or clinically significant abnormalities, two additional ECGs must be performed to confirm the safety finding. ECG safety monitoring, or a review process, should be in place for clinically significant ECG findings at baseline before administration of study treatment and during the study.

Clinically significant abnormalities must be recorded on the eCRF as either medical history/current medical conditions or AEs as appropriate.

Full details of all procedures relating to the ECG collection and reporting will be contained in a technical manual to be provided by the CRO to each investigator site.

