2.7.4 Other safety data

2.7.4.1 ECG and cardiac imaging data

All listings will be provided for each CINDU cohort separately. A listing of all newly occurring or worsening abnormalities will be provided, as well as a by-subject listing of all quantitative ECG parameters.

The following will be considered as notable values for adults: QT > 500 msec; QTcF > 450 msec (males), QTcF > 460 msec (females); QTcF change from baseline > 30 msec, >60 msec; PR > 250 msec. The following were considered as notable ECG values for adolescents: QTcF >450 msec (males), QTcF >460 msec (females); QTcF change from baseline >30 msec, >60 msec; PR >250 msec.

[figure not shown]

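### Taking the worst same-date ECG as baseline can understate QTcF change and under-flag the >30 and >60 msec criteria in the few participants with repeat baseline ECGs

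*SAP*

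**What the plan says.** SAP 2.1.1.5 first gives a general baseline rule for safety data. With several assessments on one date, "then the pre-dosing assessment closest to the dosing time" is used; if the recorded times are equal or missing, "then the averaged outcome of the duplicated assessment on that date will be used for baseline". A separate item, headed "Handling of multiple assessment on the same date, on the last date on or before treatment start date", then makes an exception for ECGs: "ECG measurements: the worst outcome of them will be used for baseline". The readable text gives no reason for the exception and does not say what worst means for QTcF, PR or heart rate. The lines after the ECG item are redacted.

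SAP 2.7.4.1 lists notable ECG values. Among them are "QTcF change from baseline > 30 msec, >60 msec", which depend on baseline, and absolute limits for QTcF, PR and, in adults, QT, which do not. It also provides a listing of newly occurring or worsening abnormalities and a by-subject listing of all quantitative ECG parameters.

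Protocol 8.4.2 sets how many ECGs exist: "Single local 12 lead ECGs will be collected at Screening (Visit 1), Week 24 (Visit 160) and unscheduled as required". Where an ECG raises a safety concern or is clinically significantly abnormal, "two additional ECGs must be performed to confirm the safety finding".

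**The concern.** At baseline, a worst-value rule works against safety detection. The maximum of several readings is high partly by chance, and a single later reading is not selected in the same way. The difference between them therefore understates the true rise.

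The participants affected are not a random subset. One ECG is scheduled at screening and one at Week 24, so same-date sets before treatment should arise mainly when the first tracing prompted the two confirmatory ECGs. The change-from-baseline flag is then weakest in people whose ECG was already in question.

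A related effect concerns new abnormalities. SAP 2.7.3 defines a newly occurring laboratory abnormality as one that was not notable, or was missing, at baseline. If ECGs follow that logic, one notable tracing out of three removes new status from a later notable value.

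The ECG item is also tied to a date, not to dosing time, and the same section says "Assessments made on Day 1 may occur before or after the first dose". The readable text therefore does not expressly exclude a post-dose Day 1 ECG from the set.

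**Working it through.** The plan states no figure for ECG baseline variability, so there is nothing to reproduce.

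**Inputs**
- Baseline ECGs per affected participant: 1 + 2 = 3 (Protocol 8.4.2), taken here to fall on one date.
- On-treatment ECGs: 1 (the scheduled Week 24 ECG).
- Thresholds: 30 and 60 msec (SAP 2.7.4.1).
- Within-person SD of QTcF, s: not in the documents. Assumed 5 to 15 msec.
- Readings assumed normal and independent, with worst taken as longest QTcF.

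**Inflation of baseline.** The expected maximum of three independent normal readings lies 3/(2√π) = 0.846 SD above their mean.

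| s (msec) | 0.846 × s (msec) |
|---|---|
| 5 | 4.2 |
| 8 | 6.8 |
| 10 | 8.5 |
| 12 | 10.2 |
| 15 | 12.7 |

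The measured change falls by the same amount on average.

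**Flagging when the true rise equals the threshold.** After subtracting the rise, the flag fires only if the on-treatment reading exceeds the baseline value. Against the mean, or against the latest single reading, symmetry gives 50%. Against the maximum, the on-treatment reading must be the largest of four exchangeable readings, so the probability is 1/4 = 25%. This holds for any s and for both thresholds.

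**Flagging above 30 msec for a larger true rise, d.**
- Mean of three: Φ((d − 30)/(s√(4/3))).
- Latest of three: Φ((d − 30)/(s√2)).
- Worst of three: ∫ φ(y) Φ(y + (d − 30)/s)³ dy.

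| True rise | s | Mean | Latest | Worst |
|---|---|---|---|---|
| 35 | 10 | 67% | 64% | 39% |
| 40 | 5 | 96% | 92% | 82% |
| 40 | 10 | 81% | 76% | 55% |
| 40 | 15 | 72% | 68% | 45% |

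**If same-day tracings are correlated.** With correlation ρ the inflation becomes 0.846 × s × √(1 − ρ). As an illustration, ρ = 0.5 and s = 10 give 8.46 × 0.707 = 6.0 msec, and the flag at a true rise equal to the threshold is about 33% instead of 25%.

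**If repeats are triggered by a high first QTcF.** Simulation with assumed values: trigger 430 or 440 msec, male screening cap 450 msec, population mean 410 msec, between-person SD 15 to 20 msec, within-person SD 8 to 12 msec. The worst-of-three baseline exceeded the true value by about 8 to 16 msec, against about 1 to 4.5 msec for the mean. At a true 30 msec rise the >30 msec flag fired in about 13 to 22%, against 37 to 45% with the mean.

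**If worst of three were also used on treatment,** the bias would cancel: 50% are flagged at a true 30 msec rise.

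**The case against.** A reader might infer that the rule hides on-treatment prolongation. The documents do not support that. The absolute limits in SAP 2.7.4.1 (QTcF above 450 or 460 msec by sex, PR above 250 msec, adult QT above 500 msec) do not use baseline. The by-subject listing shows every quantitative value, including each baseline replicate. Protocol 12.5.2 also has the central cardiologist flag QTcF above 450 or 460 msec. In the triggered-repeat simulation, 64 to 96% of affected participants with a true 30 msec rise still crossed the 450 msec limit. What is weakened is the derived change flag, which matters for someone who rises substantially but stays below the absolute limit.

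The affected group is also small, and its existence is partly inferred. Protocol 8.4.2 does not say that confirmatory ECGs fall on the same day; if they fall later, the baseline date moves and the first tracing drops out. Screening QTcF above 450 or 460 msec is an exclusion, which limits the inflation, although the text does not say which of several readings decides eligibility. The concern behind a repeat need not be QTcF. All of this stands and narrows the reach.

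Worst might mean the overall ECG interpretation and not the longest QTcF. That is possible, but the readable text does not settle it, and a programmer needs a numeric baseline to derive a change.

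A rule for on-treatment repeats may sit in the redacted lines, so none can be called missing. A worst-value rule there would offset the bias where on-treatment repeats exist, but not against a single Week 24 ECG.

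Finally, an abnormality recorded before treatment is arguably not new, and worsening abnormalities are listed too. The effect on new status is therefore a weaker point than the effect on the change flags.

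**Conclusion.** The point holds in a limited form. The SAP departs from its own general baseline rule for ECGs and, on the natural reading of worst as longest QTcF, biases QTcF change from baseline downward in participants with same-date repeat baseline ECGs. At a true rise equal to the 30 or 60 msec threshold, flagging drops from 50% to 25%. That result needs three independent baseline readings and one on-treatment reading, but no SD. The 4 to 13 msec inflation rests on an assumed SD of 5 to 15 msec and shrinks if same-day tracings are correlated. Participants with one baseline ECG are untouched.

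The practical weight in this study is low. It was terminated with 39 participants enrolled and 3 having completed Week 12. No statistical analyses will be done, and the ECG outputs in SAP 2.7.4.1 are listings. The rule is still live, because the change-from-baseline criteria remain in that section.

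**What to change.** In SAP 2.1.1.5, define baseline for quantitative ECG parameters (QTcF, QT, PR, heart rate) as the mean of the pre-dose ECGs on the last date on or before treatment start, or apply the section's general latest/average rule to ECGs. State that same-date on-treatment repeats are handled in the same way. Keep worst only for the categorical overall interpretation, and say there what it means.

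The cost is a line or two of SAP text and a small programming change, with no new data. The downside is that slightly more QTcF changes may be listed.
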